2.2 Secondary Objectives

To investigate the effect of saxagliptin treatment on serum endothelium inflammatory markers including: C-reactive protein (hs-CRP), IL-6, TNF-alpha, Leptin, Adiponectin, and fasting lipid profile ^{6, 30}

Glycemic control will be evaluated by measuring fasting blood glucose, insulin levels and HbA1c. Fasting blood glucose and insulin will be used to assess insulin resistance with HOMA-IR ³²

Adiposity will be measured using the Tanita Body Composition Analyzer scale, measured as percentage body fat ³³

Vessel health will be assessed by systolic and diastolic blood pressure and Arterial stiffness will be assessed using Vascular Flow and wave measurement equipment, SphygmoCor CP system from ATCOR. The sphygmoCor system also allows us to estimate central aortic blood pressure.

The biochemical or bio-inflammatory markers are an important marker of endothelial inflammation and dysfunction along with glycemic markers and markers of arterial stiffness.

3 ETHICAL CONSIDERATIONS

3.1 Good Clinical Practice

This study will be conducted in accordance with Good Clinical Practice (GCP), as defined by the International Conference on Harmonisation (ICH) and in accordance with the ethical principles underlying European Union Directive 2001/20/EC and the United States Code of Federal Regulations, Title 21, Part 50 (21CFR50).

The study will be conducted in compliance with the protocol. The protocol, any amendments, and the subject informed consent will receive Institutional Review Board/Independent Ethics Committee (IRB/IEC) approval/favorable opinion before initiation of the study.

All potential serious breaches must be reported to Astra-Zeneca (AZ) immediately. A serious breach is a breach of the conditions and principles of GCP in connection with the study or the protocol, which is likely to affect, to a significant degree, the safety or physical or mental integrity of the subjects of the study or the scientific value of the study.

Study personnel involved in conducting this study will be qualified by education, training, and experience to perform their respective tasks.

This study will not use the services of study personnel where sanctions have been invoked or where there has been scientific misconduct or fraud (e.g., loss of medical licensure; debarment).

3.2 Institutional Review Board/Independent Ethics Committee

Before study initiation, the investigator must have written and dated approval/favorable opinion from the IRB/IEC for the protocol, consent form, subject recruitment materials/process (e.g., advertisements), and any other written information to be provided to subjects. The investigator or sponsor should also provide the IRB/IEC with a copy of the Investigator Brochure or product labeling information to be provided to subjects, and any updates.

The investigator should provide the IRB/IEC with reports, updates, and other information (e.g., expedited safety reports, amendments, and administrative letters) according to regulatory requirements or institution procedures.

3.3 Informed Consent

Investigators must ensure that subjects or, in those situations where consent cannot be given by subjects, their legally acceptable representative are clearly and fully informed about the purpose, potential risks, and other critical issues regarding clinical studies in which they volunteer to participate.

Investigators must:

[figure not shown]
- 1) Provide a copy of the consent form and written information about the study in the language in which the subject is most proficient prior to clinical study participation. The language must be non-technical and easily understood.
- 2) Allow time necessary for subject or subject's legally acceptable representative to inquire about the details of the study.
- 3) Obtain an informed consent signed and personally dated by the subject or the subject's legally acceptable representative and by the person who conducted the informed consent discussion.
- 4) Obtain the IRB/IEC's written approval/favorable opinion of the written informed consent form and any other information to be provided to the subjects, prior to the beginning of the study, and after any revisions are completed for new information.
- 5) If informed consent is initially given by a subject's legally acceptable representative or legal guardian, and the subject subsequently becomes capable of making and communicating their informed consent during the study, then consent must additionally be obtained from the subject.
- 6) Revise the informed consent whenever important new information becomes available that is relevant to the subject's consent. The investigator, or a person designated by the investigator, should fully inform the subject or the subject's legally acceptable representative or legal guardian, of all pertinent aspects of the study and of any new information relevant to the subject's willingness to continue participation in the study. This communication should be documented.

The rights, safety, and well-being of the study subjects are the most important considerations and should prevail over interests of science and society.

4 INVESTIGATIONAL PLAN

4.1 Study Design and Duration

Study Schema, 42 Type 2 diabetic Subjects Aged 40-70 on stable dose of Metformin

+/- 3 days for visits Wk 0 Wk 6 and Wk 12, if the particular day is not feasible

*Assessed at week 0, 6 and 12: Biochemical and cellular markers of endothelial function and Pulse wave analysis and velocity (PWA and PWV).

Available related studies and Expected Results: Studies measuring changes to EPCs in type 2 diabetes patients are very limited. To the best of our knowledge there are no studies examining the effect of saxagliptin in early diabetes on patient's CD34/KDR+ve cells and comparing that to the effect of lifestyle + metformin on CD34+ve cell population. The regenerative potential of EPC is thought to be due to direct incorporation into vascular endothelium and/or the secretion of angio-supportive factors to enhance endothelial repair and function^{17, 18, 19}. Our studies and others^{11, 12, 34}, have shown that various disease states, including those seen in diabetes, can deplete and damage EPC, thereby diminishing their regenerative potential. The inability to maintain or repair damaged endothelial tissue leads to cumulative vascular dysfunction and cardiovascular disease.

We hypothesize that monitoring *number, function and gene expression of endothelial progenitors will allow us to quantify cardiovascular disease risk at the onset and regenerative potential post intervention at a cellular level. It will also help us to identify and correlate the best endothelial function bio-chemical inflammatory marker as an early indicator of cardiovascular disease progression in early type 2 diabetes.*

Therefore, studying the effects of Saxagliptin which can increase SDF1 alpha levels and possibly CXCR4 receptor expression as an intervention on the number and health of EPCs may not only provide insight on the biological role of these cells, but they can be used as a tool to study vascular biology and lastly can be a potential target for prevention of diabetes vascular complications.

We expect to establish that saxagliptin improves endothelial function that is EPC number, function, gene expression and bio-inflammatory markers beyond its glycemic control effect in type 2 diabetes patients.

Saxagliptin 5 mg or placebo will be added to patients who have type 2 diabetes diagnosed less than 8 years with HbA1C of 6 to 9 % (both inclusive) while being on lifestyle modification and Metformin (≥ 1.0 to ≤ 2 gm/d orally).

Our study population will include equal numbers of adult male and female Type 2 diabetes (T2DM) patients aged 40-70 years, enrolled in both arms of the study.

Patients will be treated with 5 mg of Saxagliptin or placebo with lifestyle modification for 12 weeks. This time interval has been previously shown to be adequate to observe changes to Endothelial Progenitor Cells (EPCs)^{5,6}.

4.2 Study Population

For entry into the study, the following criteria MUST be met.

4.2.1 Inclusion Criteria

1) Signed Written Informed Consent

- Before any study procedures are performed, subjects will have the details of the study described to them, and they will be given a written informed consent document to read. Then, if subjects consent to participate in the study, they will indicate that consent by signing and dating the informed consent document in the presence of study personnel.

2) Target Population

- Subjects with a diagnosis of Type 2 diabetes mellitus within the previous 8 years using criteria of the American Diabetes Association.
- Currently treated with no hypoglycemic agents other than a stable dose (>3 months) of metformin (≥ 1.0 to ≤ 2 grams daily).
- HbA1C between 6% and 9% (both inclusive)
 - BMI 25-39.9 kg/m² both inclusive.

3) Age and Reproductive Status

- Men and women, 40 to 70 years of age.
- **Reproductive Status: Definition of Women of Child-Bearing Potential (WOCBP).** WOCBP comprises women who have experienced menarche and who have not undergone successful surgical sterilization (hysterectomy, bilateral tubal ligation, or bilateral oophorectomy) or who are not post-menopausal (see definition below).

Post-menopause is defined as:

- Women who have had amenorrhea for \geq 12 consecutive months (without another cause) and especially with a documented serum follicle-stimulating hormone (FSH) level $>$ 35 mIU/mL.
- Women who have irregular menstrual periods and a documented serum FSH level $>$ 35 mIU/mL.
- Women who are taking hormone replacement therapy (HRT).

The following women are WOCBP:

- Women using the following methods to prevent pregnancy: Oral contraceptives, other hormonal contraceptives (vaginal products, skin patches, or implanted or injectable products), or mechanical products such as intrauterine devices or barrier methods (diaphragm, condoms, spermicides).
- Women who are practicing abstinence.
- Women who have a partner who is sterile (e.g., due to vasectomy). WOCBP must be using an acceptable method of contraception to avoid pregnancy throughout the study and for up to 4 weeks after the last dose of study drug in such a manner that the risk of pregnancy is minimized.
- WOCBP must have a negative serum or urine pregnancy test result (minimum sensitivity 25 IU/L or equivalent units of HCG) within 0 to 72 hours before the first dose of study drug.
- Women must not be breast-feeding.

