Exclusion Criteria:	
Patients with:
 
 1. Contraindications for moderate exercise 2. Implanted devices (e.g., pacemakers) that may interact with Tanita scale 3. Previous coronary or cerebrovascular event within 6 months of screening or active or clinically significant coronary and/or peripheral vascular disease 4. Low hematocrit (< 28 UNITS). 5. Pre-existing liver disease and/or ALT and AST $>2.5 \times$ UNL 6. Kidney disease at levels defined by: serum creatinine levels ≥ 1.5 mg/dL for men, ≥ 1.4 mg/dL for women, estimated CrCl ≤ 50 mL/min 7. History of pancreatitis, or cancer (except basal cell carcinoma) 8. Statin use started (or dose change) in the last 3 months, 9. Use of oral or injectable anti-diabetic medication other than Metformin 10. Daily use of a consistent long-term steroid medication (oral, inhaled, injected) within the last 3 months 11. Systolic BP > 140 mmHg and Diastolic BP > 90 mmHg at screening visit. 12. Active wounds or recent surgery within 3 months. 13. Inflammatory disease, or chronic current use of anti-inflammatory drugs within the last 3 months. 14. triglycerides >400 mg/dL 15. untreated hyper/hypothyroidism 
Additionally, patients who are active smokers, patients who are pregnant, nursing women, and post-menopausal women who are on hormone replacement therapy will be excluded.
 
Patients on low dose oral contraceptives will be allowed to participate as these formulations contain lesser amount of estrogens.

----------------------------	---

Criteria for Evaluation: (Efficacy, safety, stopping rules, etc.)	Subjects will be screened at week -4, then evaluated for end points at weeks 0, 6 and 12. Study participation will be stopped for adverse effects at the discretion of the study investigator. Subjects may stop study participation at any time and for any reason.
Statistics:	The total sample size requested, accounting for attrition over the 12-week period, is 20 subjects per group or 40 subjects total. Sample size estimates were based on the effects of exercise on CD34+/KDR+ cells as described in the literature. The effect of a single session, as well as extended training, on healthy subjects or those with existing cardiovascular conditions appears to increase the CD34+/KDR+ cells. This will provide 73% power (see statistics section). A p-value of less than 0.05 will be considered statistically significant.

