1 INTRODUCTION

Type 2 diabetes is a national epidemic ^{1,2} with significant macro and microvascular complications³. Insulin resistance in prediabetes and early and late diabetes are associated with endothelial dysfunction⁴.

A few studies indicate that EPCs can act as a suitable bio-marker ⁵⁻⁷ for monitoring cardiovascular morbidity. In this proposal we suggest that EPCs or CD34 positive cells can act as a suitable cellular biomarker for estimating and following endothelial dysfunction in early type 2 diabetes patients.

EPCs have been used as a regenerative tool in ischemic myocardium and diabetic wound healing ⁸⁻¹³. Endothelial dysfunction with associated inflammation may be a consequence of excess super-oxide presence in a setting of diabetes which is a pro-oxidative stress condition causing EPC dysfunction and senescence¹⁴. Therefore monitoring EPC number, function and gene expression may serve as a very useful cellular bio-marker for cardiovascular complications in early type 2 diabetes.

Though lifestyle modification has been proposed as a main stay for prevention and treatment of early type 2 diabetes, ^{2, 15-19} several new therapies for diabetes have been developed in recent years². Incretins and incretin mimetics appear to hold promise. Oral DPP-4 inhibitors have been shown to increase EPCs in patients with type 2 diabetes ²⁰ reportedly via SDF-1 alpha up-regulation. Interestingly, up-regulation of SDF-1 alpha and vascular endothelial growth factor (VEGF), both chemotactic factors increase mobilization and recruitment of EPCs in the face of acute ischemic injury for repair and regeneration.²¹⁻²⁴.

Several studies have shown positive effect of incretins (Glucagon like peptide, GLP-1) and incretin receptor agonists (GLP-1 receptor agonists) on cardiovascular risk factors in type 2 diabetes patients^{20,25} and even in patients with chronic heart failure and left ventricular dysfunction who do not have diabetes^{26,27}.

DPP-4 Inhibitors may have cardio-protective effects of their own, as they increase bio-availability of endogenous GLP-1. They improve blood flow and nitric oxide production in endothelium^{28, 29}. These are unique properties not demonstrated by other oral diabetes medications ²⁸. The mechanism underlying these effects may be mediated by increased nitric oxide bioavailability but is not completely known. It is possible that Saxagliptin, a member of DPP-4 inhibitor group of drugs may be able to improve number and function

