4.2.2 Exclusion Criteria

- Type 1 diabetes mellitus
- History of diabetic ketoacidosis or hyperosmolar nonketotic coma
- Hemoglobinopathies with low hematocrit (hematocrit below normal limits that may impair exercise tolerance) or abnormal CBC
- History of pancreatitis, or cancer (except basal cell carcinoma)
- Previous coronary or cerebrovascular event within 6 months of screening or active or clinically significant coronary and/or peripheral vascular disease

- Statin use started (or dose change) in the last 3months,
- Daily use of oral or injectable anti-diabetic medication other than Metformin
- use of any form of steroid medication (oral, inhaled, injected or nasal) within the last 3 months
- Systolic BP> 140 mmHg and Diastolic BP> 90mmHg at screening visit.
- Active wounds or recent surgery within 3 months
- Inflammatory disease, or current use of anti-inflammatory drugs
- Untreated hyper/hypothyroidism
- Contraindications for moderate exercise
- Implanted devices (e.g., pacemakers) that may interact with Tanita scale

Physical and Laboratory Test Findings

- Pre-existing liver disease and/or ALT and AST >2.5X's UNL,
- serum creatinine levels ≥ 1.5 mg/dL for men, ≥ 1.4 mg/dL for women, estimated CrCl ≤ 50 mL/min)
- Triglycerides >400 mg/dL

Allergies and Adverse Drug Reactions

- Subjects with a history of any serious hypersensitivity reaction to saxagliptin or DPP-4 inhibitor.

Sex and Reproductive Status

- WOCBP who are unwilling or unable to use an acceptable method to avoid pregnancy for the entire study period.
- Women who are pregnant or breastfeeding.

See Section on WOCBP above (Section 4.2.1, item # 3.)

Prohibited Treatments and/or Therapies

- Treatment with systemic cytochrome P450 3A4 (CYP 3A4) inhibitors

Other Exclusion Criteria

- Prisoners or subjects who are involuntarily incarcerated.
- Subjects who are compulsorily detained for treatment of either a psychiatric or physical (e.g., infectious disease) illness.

Additionally, patients who are active smokers, patients who are pregnant, nursing women, and post menopausal women who are on hormone replacement therapy will be excluded. Patients on low dose oral contraceptives will be allowed to participate as these formulations contain lesser amount of estrogens.

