²⁰where Sitagliptin was compared to placebo with endothelial progenitor cells as a outcome measure in patients with type 2 diabetes over 4 weeks. Though our study is over 12 weeks we do not anticipate significant drop in HbA1C in between the two groups in this relatively short time period to act as a confounding factor on CD34+ cell number, function and gene expression. Most clinical studies looking at HbA1C reduction were of a much longer duration of 6 months or above and most DPP-4 inhibitor studies are with animal EPCs where comparison with human CD34+ population is difficult to make. In one study⁵⁸ where saxagliptin was used for 12 weeks in drug-naïve type 2 diabetes patients there was placebo-subtracted HbA1c reduction noted of 0.45-0.63%. It showed mean placebo-subtracted reductions in fasting serum glucose of 20 mg/dL. From our laboratory studies of in vitro human EPC studies we do not think glucose level change of 20 mg/dL is significant enough to account for changes in EPC number, function and gene expression. However we will take this possibility into account during statistical analysis of the results between the saxagliptin and placebo groups.

Lifestyle Intervention for Type 2 diabetes patients²:

To keep uniformity within the cohort regarding lifestyle during the length of the study duration, all patients at entry will ideally receive dietary advice from the research coordinator, a diabetes educator, a registered dietitian (as per American Diabetes Association clinical guidelines²), specifically geared towards type 2 diabetes patients. They will be advised to adhere to 150 minutes of weekly aerobic exercise (50-70% of maximal heart rate) as best as possible. Patient's activity will be monitored using accelerometers and will be downloaded at regular intervals by the research coordinator.

Subjects will be taking 5.0 mg of Onglyza (saxagliptin) or placebo. We choose to use the maximum approved dose of saxagliptin in order to discern a definite effect.

Visits with outcome measurements will be scheduled for morning following overnight 10 hours fast to reduce diurnal variability, and clinical parameters will be obtained at scheduled office visits as depicted in the study schema and will be measured at each outcome visit as follows:

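### The limit on other glucose-lowering drugs has three wordings and no look-back, so a patient who stopped a DPP-4 inhibitor shortly before screening is eligible

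*Combined protocol and SAP*

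**What the plan says.** The restriction on other glucose-lowering drugs is worded in three ways:

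- **Inclusion (synopsis, section 4.2.1, and Patient Definition and Selection in section 6):** current treatment. Section 4.2.1 reads "Currently treated with no hypoglycemic agents other than a stable dose (>3 months) of metformin".
- **Exclusion, synopsis:** "Use of oral or injectable anti-diabetic medication other than Metformin".
- **Exclusion, section 4.2.2:** "Daily use of oral or injectable anti-diabetic medication other than Metformin".

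The same section 4.2.2 list does give time windows for other exposures: "Statin use started (or dose change) in the last 3months", "use of any form of steroid medication (oral, inhaled, injected or nasal) within the last 3 months", and surgery within three months. A history with the tested class appears there only as an allergy criterion: "Subjects with a history of any serious hypersensitivity reaction to saxagliptin or DPP-4 inhibitor".

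On what the class does, section 1 states: "Oral DPP-4 inhibitors have been shown to increase EPCs in patients with type 2 diabetes". Section 6 describes the same cited study as one where "Sitagliptin was compared to placebo with endothelial progenitor cells as a outcome measure in patients with type 2 diabetes over 4 weeks". CD34+ cell number is among the primary measures, first sampled at week 0.

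The week -4 paragraph in section 6 has eligibility verified at screening and allows four weeks to reach a lifestyle steady state. The week 0 paragraph has the inclusion criteria checked again.

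**The concern.** The plan protects the baseline against recent changes in statins, steroids and surgery, but not against recent use of the class it is testing. As written, a patient on long-stable metformin who stopped another DPP-4 inhibitor, or another incretin drug, shortly before the week -4 visit meets every criterion. The baseline cell sample follows about four weeks later. The documents do not say whether the cell effect has gone by then.

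Two uses of the week 0 value are exposed. The mixed model treats it as the first outcome point, so an excess there enters the fitted slope. And section 2.1 frames the cellular objective as change before and after saxagliptin. That is a within-patient contrast, which randomisation does not protect.

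**Working it through.** **1. Is there a look-back anywhere?** Reading the lists side by side:

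| Exposure | Window in the eligibility text |
|---|---|
| Metformin dose | stable for more than 3 months |
| Statin start or dose change | 3 months |
| Steroids | 3 months |
| Surgery | 3 months |
| Other glucose-lowering drugs | none (current / use / daily use) |

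In section 4.2.1 the three months stand in brackets after the metformin dose and do not govern the other agents.

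**2. The plan's own figures (section 8).** Inputs: slopes of 4 and 5 cells per week, SD 15, correlation 0.60, visits at weeks 0, 6 and 12, 18 per group.

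- Planned difference: (5 - 4) x 12 = 12 cells.
- Sxx = 36 + 0 + 36 = 72. Slope variance per patient: v = 225 x (1 - 0.60) / 72 = 1.25.
- SE of the slope difference: sqrt(2 x 1.25 / 18) = 0.373. Over 12 weeks: 12 x 0.373 = 4.47 cells.
- Power at one-sided 0.05: Phi(1/0.373 - 1.645) = 0.85, against the stated 0.84. The two-sided value is 0.765. The sidedness is a separate matter; the match is used here only to confirm the variance inputs.

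**3. How a week 0 excess enters the analysis.** Suppose a patient starts d cells above the level they would have had without the earlier drug, and weeks 6 and 12 are unaffected. The fitted slope changes by (0 - 6) x d / 72 = -d/12 per week, or -d over 12 weeks. With time as indicators and baseline as reference, the week 12 change also moves by -d. The excess therefore passes in full into the 12-week change.

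**4. Chance imbalance between arms.** The residual excess and the numbers of recent users are assumptions; neither is in the documents. Shift in the difference = (extra recent users / 18) x d.

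- Low: 2/18 x 6 = 0.67 cells, 6% of 12 and 0.15 SE.
- High: 3/18 x 12 = 2.0 cells, 17% of 12 and 0.45 SE.

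The shift can go either way. If 4 of 40 patients were recent users, the chance of a 3:1 or 4:0 split is 0.605.

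**5. Added noise.** With a share f of recent users, the slope variance becomes 1.25 + f(1 - f)(d/12)^2. One-sided power at 18 per group, starting from 0.85:

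| f | d = 6 | d = 12 | d = 24 |
|---|---|---|---|
| 5% | 0.848 | 0.839 | 0.804 |
| 10% | 0.845 | 0.828 | 0.764 |
| 20% | 0.840 | 0.811 | 0.704 |

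The loss is negligible except where recent users are common and the residual excess is large.

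**6. Pre/post comparison.** The mean rise in the saxagliptin arm is understated by f x d in expectation: 0.05 x 6 = 0.3 cells up to 0.20 x 24 = 4.8 cells, against the 5 x 12 = 60 cells that the planning slope implies.

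**The case against.** **Points that stand.**

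- Randomisation balances earlier drug use in expectation, so the between-arm comparison is not systematically biased.
- A patient who stopped just before screening has about four weeks off the drug by week 0. The documents report a rise on treatment and are silent on how long it lasts after stopping. The 6 to 24 cells used above are therefore pure assumption, and 12 is already the whole planned difference.
- The three-month figure is borrowed by analogy. Nothing ties it to recovery of cell counts.

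**Points that help only in part.** Medical history is scheduled, and section 8 adjusts for characteristics found unbalanced on inspection. But no item asks for earlier incretin-class use. A covariate entered as a main effect would also leave a week 0 excess in the group-by-time term, and adjustment between groups does not repair the pre/post contrast.

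**Stronger readings that the text does not support.**

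- A reader might infer that a drug stopped during the run-in satisfies the criteria, because the Time and Events Schedule marks Inclusion/Exclusion only at week 0. The week -4 paragraph has eligibility verified at screening, and the week 0 check asks whether patients still qualify. The same table marks consent only at week 0, although consent must precede every procedure, so it is weak evidence on timing.
- A reader might infer that the daily-use wording admits someone currently on a weekly injectable. That patient fails the inclusion criterion, and all criteria must be met.

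**Conclusion.** The gap in the text is real: there are three wordings, none with a look-back, and a recent user of the tested class is eligible about four weeks before the baseline sample. The consequence is modest. It consists of some added noise, possible chance imbalance at week 0 that carries in full into the fitted 12-week change, and a pre/post saxagliptin comparison that is understated if any class effect persists.

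The size cannot be established, because the documents give neither the share of recent users nor the persistence of the effect after stopping. On the assumed inputs the imbalance is 0.7 to 2.0 cells against a standard error of about 4.5. A reader might conclude that the trial turns into a comparison of withdrawal with resumption of the class. The documents do not support that: it could describe at most those patients who were recent users, and randomisation spreads them across both arms in expectation.

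This is a cheap improvement worth making in a trial of about 20 per arm, not a threat to its validity.

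**What to change.** Replace the three wordings with one criterion in the synopsis, section 4.2.1 and section 4.2.2, and align the Patient Definition and Selection paragraph: no glucose-lowering drug other than metformin, taken at any frequency, within a stated look-back before the week -4 screening. The three months already used for metformin dose and statin changes would be a consistent choice; the protocol should say that it is chosen for consistency. Add to the medical history a record of any earlier DPP-4 inhibitor or GLP-1 receptor agonist use, with stop date, so that balance between arms can be described.

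The cost is a short eligibility amendment and one history item. A few candidates will be deferred or not enrolled; candidates who have been on metformin alone are unaffected.
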